9.3 CONFIDENTIALITY

The Chief Investigator will preserve the confidentiality of participants taking part in the study and is registered under the Data Protection Act.

9.4 INDEMNITY

Imperial College London holds negligent harm and non-negligent harm insurance policies, which apply to this study.

9.5 SPONSOR

Imperial College London will act as the main Sponsor for this study. Delegated responsibilities will be assigned to the NHS trusts taking part in this study.

9.6 FUNDING

This project is funded by the National Institute for Health Research HTA (project number 11/129/197).

9.7 QUALITY ASSURANCE AND CONTROL

The study may be subject to inspection and audit by Imperial College London under their remit as sponsor and other regulatory bodies to ensure adherence to GCP and the NHS Research Governance Framework for Health and Social Care (2nd edition). Quality Control will be performed according to the requirements of the Risk Assessment performed by ICTU. The study may be audited by a Quality Assurance representative of the Sponsor. All necessary data and documents will be made available for inspection.

10. STUDY MANAGEMENT

The study will be coordinated by a trial manager based at ICTU reporting to the Clinical Coordinators (MG and RB) and the Chief Investigator (AD). The Clinical Coordinators will liaise with local principal investigators (L-PI) to ensure that the trial is conducted locally according to protocol and in an expeditious manner. The organisational structure and responsibilities are outlined below.

10.1 PRINCIPAL INVESTIGATORS

The chief investigator and clinical coordinators have overall responsibility for:

- Design and conduct of the study
- Preparation of the Protocol and subsequent revisions
- Managing the Trial Coordinating Centre
- Development of SOPs

10.2 TRIAL STEERING COMMITTEE

A Trial Steering Committee (TSC) will be established in line with HTA guidance, consisting of the chief Investigator, clinical coordinators, trial manager, trial statistician, patient representative, an independent chair and at least 1 other independent member will be formed and will meet on a 6-monthly basis to discuss trial progress. The TSC is responsible for:

- Agreement of the final Protocol
- Agreeing the Data Analysis Plan
- Reviewing progress of the study and, if necessary, agreeing changes to the Protocol
- Reviewing new studies that may be of relevance
- Review and approval of study reports

10.3 DATA MONITORING COMMITTEE

The independent Data Monitoring Committee (DMC) will be established in line with HTA guidance will focus on the rights, safety and wellbeing of study participants. DMC responsibilities are:

- Reviewing unblinded interim data according to the schedule agreed by all DMC members.
- Advising the Steering Committee if, in their view, the randomised data provide evidence that may warrant early termination for either safety or efficacy.

10.4 TRIAL COORDINATING CENTRE

The Trial Coordinating Centre (TCC) is responsible for the overall coordination of the Study, including:

- Study planning and organisation of Steering Committee meetings
- Agreement of each local recruitment plan
- Contractual issues with local study sites
- Ethics Committee applications
- Design, implementation and maintenance of IT systems for the study
- Auditing and monitoring of overall progress of the study
- Clinical safety monitoring (including the reporting of all “related” SAEs to the Chair of the DMC and Ethics Committee)
- Liaison with the Data Monitoring Committee and (where appropriate) with regulatory authorities and other outside agencies
- Responding to technical and administrative queries from local study sites

10.5 LOCAL STUDY SITES

The local principal investigators (L-PI) and clinical staff at the local study sites are responsible for:

- Obtaining local R&D and management approval (aided by the Trial Coordinating Centre)
- Provision of adequate clinic space and the identification of potentially eligible participants
- Conducting study procedures and follow-up according to study protocol
- Dealing with routine enquiries from participants and their families
- Obtaining appropriate information to confirm potential primary and secondary study endpoints
- Attend annual EVRA Study Collaborator Meetings to discuss study progress

11. DOCUMENT RETENTION

Data will be stored for a minimum of 10 years following completion of this trial in accordance with the Imperial College JCRO Archiving Study Documents SOP. Data generated by this work will be processed in accordance with the Data Protection Act 1998.

12. PUBLICATION POLICY

The findings will be disseminated to General Practitioners, nursing staff, surgeons and other health care professionals at regular research and educational meetings organised at local, regional, national and international levels. All analyses will be performed in compliance with a predefined analysis plan. The chief investigator, clinical coordinators and trial coordinator will be responsible for drafting the main reports from the study. Draft copies of any manuscripts will be provided to local principal investigators at each local study site, TSC members and all other collaborators for review prior to publication. The results will be put forward for critical peer review with a view to publication in relevant medical and nursing journals.

Appendix 1: Summary of assessments and follow-up visits

Time point	Estimated duration (mins)	Clinical evaluation*	Telephone follow-up**	Wound review/photo /tracing***	Collection of further endovenous intervention / duplex report	Venous duplex	Randomisation	Consent	Health Questionnaires (EQ-5D, SF-36, AVVQ)
Screening Visit	45	X				X		X ^a	
Baseline Visit	60-90	X		X***			X	X ^b	X
1 month	30		X						
6 weeks	60-90	X		X ^{?****}		X ^c			X
2 months	30		X	X [?]					
3 months	30		X	X [?]					
4 months	30		X	X [?]					
5 months	30		X	X [?]					
6 months	30		X	X [?]					X
7 months	30		X	X [?]					
8 months	30		X	X [?]					
9 months	30		X	X [?]					
10 months	30		X	X [?]					
11 months	30		X	X [?]					
12 months	30		X	X [?]					X
Extension follow-up Oct18 to Mar 19	240	X ^d	X		X			X ^e	X

*. Demographic details (age, sex, ethnicity), Pregnancy test for woman of child bearing potential. General clinical details (body mass index, ankle brachial pressure index – performed within previous 4 weeks, comorbidities, medication history). Ulcer details (duration, progression, previous ulcer history, size of current ulcer – using photography and planimetry). Details of venous disease (previous deep vein thrombosis, previous venous interventions, pattern of venous reflux on duplex)

. Ulcer healing assessment, compression type, AE assessment, Concomitant medications, health resource use. *tracing only performed at baseline & 6 weeks

a. Approached b Taken c. Only for those who have early endovenous treatment d. review of clinical notes only e. patients will not be reconsented as already consented for longer term follow-up at outset but will be asked if they wish to continue

?dependant on whether the ulcer has healed photo will be taken at verification visit and taken weekly for 4 weeks, unless otherwise confirmed by the trial manager. Once the ulcer has healed the patient will still be followed up with monthly phone calls.

## 1. Introduction

Chronic leg ulcers are open “sores” on the lower limbs situated between the ankles and knees, which fail to heal within 6 weeks. The underlying cause of leg ulceration in over 70% of cases is lower limb venous dysfunction, sometimes evident as varicose veins but often undetectable by visual examination alone. The estimated overall prevalence of active venous ulceration is as high as 1.5 to 1.8 per 1000 population, increasing to 3.8 per 1000 population in those over 40 years of age. As patients with venous ulceration usually suffer episodes of recurrence between periods when the ulcer remains healed, the number of patients with a high risk of ulceration may actually be 4-5 fold higher.

Venous ulcers are characterised by protracted healing times. Despite some recent advances in the management of patients with venous ulcers, 24 week healing rates in published randomized trials are around 60-65%, and the true population healing rates are likely to be significantly lower.

For over a century, the treatment of superficial venous reflux has involved operative ligation and surgical stripping of the vein and avulsion of bulging varicose veins. Until recent years, open surgery has been considered the definitive treatment option for superficial venous reflux. However, the operation usually requires general anaesthesia and patients often suffer discomfort, bruising and significant time off work in the post-operative period. In addition, long-term studies have also identified significant complications of open surgery. In response to this high complication rate and a growing patient desire for less invasive treatments, a range of novel, minimally invasive endovenous treatment options have been developed and have gained in popularity over the last decade. Non-randomized studies suggest that outcomes may be improved by treating underlying superficial reflux using the latest technologies, but there is no robust evidence to support early intervention. Therefore, we believe that there is a cogent argument for conducting this trial at this time.

### 1.1 Study Objectives

#### *Primary Objective*

To study the clinical and cost effectiveness of early endovenous treatment of superficial venous reflux in addition to standard care compared to standard care alone in patients with chronic venous ulceration.

### ***Secondary Objectives***

- To assess the ulcer free time to 1 year
- To assess the technical success of endovenous interventions

### **1.2 Study Population**

Patients with leg ulceration referred to secondary care as part of the standard care pathway.

### **1.3 Study Design**

The EVRA ulcer trial is a pragmatic, multicentre randomized clinical trial with participants randomized 1:1 to either:

‘Standard’ therapy consisting of multilayer elastic compression bandaging / stockings with deferred treatment of superficial reflux (usually once the ulcer has healed)

Early endovenous treatment of superficial venous reflux (within 2 weeks) in addition to standard therapy

### **1.4 Study Outcomes**

#### ***Primary Outcome***

The primary outcome measure will be time to ulcer healing (from date of randomization to date of healing). For the purposes of this study, ulcer healing is defined as complete re-epithelialisation of all ulceration on the randomised (reference) leg in the absence of a scab (eschar) with no dressing required.

#### ***Secondary Outcomes***

- Ulcer Healing Rate: 24-week healing rate will be reported in addition to time to ulcer healing.
- Ulcer reoccurrence / Ulcer Free Time: Will be calculated up to 1 year for each study arm.
- Quality Of Life (QoL): Disease specific (AVVQ) and generic (EQ5D & SF36) quality of life assessments will be compared at 6 weeks post randomisation, 6 months and 12 months.
- Health Economic Assessment
- Other Markers of Clinical Success: The Venous Clinical Severity Score (VCSS) and will be assessed at 6 weeks. In addition, the incidence of complications related to the endovenous intervention as well as the presence of residual / recurrent varicose veins will also be assessed at 6 weeks.

## 1.5 Study Sample Size

The sample size calculation for this study was based on the primary outcome of ulcer healing. According to previous published literature, the 24-week healing rate in patients randomised to standard treatment (compression alone) was approximately 60%, while the 24-week healing rate of early treatment of superficial venous reflux may be as high as 82%.

In order to calculate a sample size for this study, we estimate a benefit associated with early treatment of around 15%. To identify a difference in 24-week healing rates of 15% between the two groups (60% vs 75%) with 90% power and allowing for 10% dropout, the study will therefore require 416 subjects (208 per group).

## 1.6 Randomisation

The normal clinical team will make initial contact with potentially eligible patients at the referral visit.

Those who consent will be registered on the InForm ITM (Integrated Trial Management) System, a web-based data entry system, which is maintained by ICTU, and their eligibility for the study confirmed. A randomization list will be loaded onto the InForm system for each centre (as stratification will be by centre) before recruitment commences, having been prepared

in advance by a statistician who is independent of the study. Each potential participant, if confirmed to be eligible, will be assigned the next available entry in the appropriate randomization list (i.e. without foreknowledge). Thereafter, treatment allocation will not be blinded (with the exception of assessment of ulcer healing). For patients with bilateral venous ulceration, the worst leg (according to the patient) will be designated the ‘reference leg’. Interventions may be performed on both legs, if deemed appropriate by the responsible clinician.

### 1.7 Schedule of Time

The study started on 24th October 2013 and is expected to recruit for about two years and follow up for another year after the recruitment of last patient. The overall study timetable is summarised in Figure 1. The independent Data Monitoring Committee (DMC) meeting will be scheduled yearly with a Chairman’s review every 6 months.

[figure not shown]

Figure 1 EVRA study Gantt chart

## 2. General Considerations

### 2.1 Analysis Strategy

All the primary analyses will be on an intention-to-treat basis. Histograms and boxplots will be used to check the distribution and possible outliers for continuous variables. Mathematical transformations will be applied, where appropriate, in order to render the continuous variables

distribution normally distributed. Continuous variables that follow an approximately normal distribution will be summarised using means and standard deviations. Skewed continuous variables will be summarised using medians and inter-quartile ranges. Categorical variables will be summarised using frequencies and percentages.

The primary outcome is time to complete healing and we will test the hypothesis that there is no difference in this between the control and intervention groups using a Cox model with study centre as a random effect. Kaplan-Meier survival curves will also be presented. As a subsidiary analysis we will investigate the effect of potential confounders (age, ulcer chronicity and ulcer size) on the treatment effect and time to complete healing using Cox regression, again with centre included in the Cox regression analysis as random effect (Table 9).

For the secondary outcome of ulcer free time, multiple regression (ordinal, if not normally distributed) will be used to adjust for the above covariates.

The quality of life (QoL) data will be summarised across baseline, 6-week, 6-month and 12-month after randomisation for both arms by means and 95% confidence intervals (CI) or median and inter quartiles, depending on the distribution of the data.

Health economic assessment will be carried by the trial health economist and thus will not be included in this statistical analysis plan.

## **2.2 Definition of Population for Analysis**

The study population will comprise all participants who were randomised. A secondary per-protocol analysis will also be carried out after excluding patients with protocol violations. For the analysis of ulcer free time, the population for analysis will be patients with complete follow-up data only. This is because ulcer free time to one year depends on the time of primary ulcer healing and duration of recurrent ulcer (for example, patients with ulcer free time of 0 day may have an unhealed primary ulcer at 1 year follow-up, or may have withdrawn from the study after healing at month 1, or may have withdrawn from the study after healing at month 11). By adding this constraint some bias may have been introduced (as the analysis will have been based on complete cases only) but ulcer free time will have only one interpretation. As a

sensitivity analysis, the analysis of ulcer free time will therefore be repeated using all the patients, irrespective of length of follow up. This should give a very conservative estimate of the treatment effect.

### **2.3 Data Management**

Data is collected and managed using InForm: an electronic data capture system built around an Oracle database. The InForm system includes validation rules for data entry to help ensure data accuracy, and has a full audit trail of data entry and changes. Data queries will be raised for inconsistent, impossible or missing data.

### **2.4 Missing Data**

There will be no data imputation for missing data in the primary endpoint (time to healing) and the secondary endpoints of 24-week healing rate and ulcer free time. However, the level and pattern of the missing data in the baseline variables and outcomes will be reported. The potential causes of any missingness will be investigated and documented as far as possible. Any missing data will be dealt with using methods appropriate to the conjectured missingness mechanism and level of missingness.

### **2.5 Level of Significance**

The primary outcome and secondary outcomes will be tested using a two-tailed hypothesis test with a 5% significance level. For secondary outcomes, there will be no adjustment for multiple testing.

### **2.6 Losses to Follow-up and Withdrawals**

All the primary analyses will be performed on an intention-to-treat basis. Only patients willing to undergo either immediate or delayed superficial venous ablation with compression bandaging are randomised. All randomised participants will be followed-up for one year (irrespective of whether or not they underwent allocated treatment). For those participants unable or unwilling to attend follow-up appointments, home-visits or follow-up by community nurses may be considered.

Subjects who die, withdraw from the study, or are lost to follow-up before ulcer healing will be censored in the Kaplan Meier and Cox regression analyses at last follow-up visit.

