1.1.2 Treatment options for superficial venous reflux

For over a century, the treatment of superficial venous reflux has involved operative ligation and surgical stripping of the vein and avulsion of bulging varicose veins¹⁵. Until recent years, open surgery has been considered the definitive treatment option for superficial venous reflux. However, the operation usually requires general anaesthesia and patients often suffer discomfort, bruising and significant time off work in the post-operative period. Long-term studies have also identified significant complications of open surgery including nerve damage and recurrence of varicose veins, seen in over 60% of patients at 11 years in one randomised study¹⁶.

In response to this high complication rate and a growing patient desire for less invasive treatments, a range of novel, minimally invasive endovenous treatment options have been developed and have gained in popularity over the last decade. Interventions such as ultrasound guided foam sclerotherapy (UGFS)¹⁷, endovenous laser (EVLA)¹⁸ or radiofrequency ablation (RFA)¹⁹ can be performed using local anaesthesia in an outpatient setting. These treatments involve cannulation of the vein to be treated (usually under ultrasound guidance) and obliteration of the venous channel by either chemical ablation (using foam sclerosant), or thermal ablation (using a laser or radiofrequency fibre). Numerous randomised studies have demonstrated that endovenous modalities are, at worst, comparable to open surgery in terms of recurrence (and likely to be better), but clearly superior in terms of pain, bruising and other early complications²⁰⁻²². Each of the different endovenous modalities has advantages and potential disadvantages, although all are less invasive than traditional open surgery. This is of particular relevance to patients with

chronic venous ulceration, who are often elderly, have extensive co-morbidities and may be reluctant to undergo surgical procedures involving general anaesthesia. Endovenous techniques can also be performed without discontinuing anti-coagulation therapy, which is increasingly prescribed in this patient population.

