
#### 4.5 Ulcer Free Time to 1 year and 24-week Ulcer Healing Rate

Table 7 summarises the ulcer free time to 1 year and 24-week ulcer healing rate between the two arms. In the case that a patient is dead, withdrawn or lost to follow-up before 1 year, ulcer free time will be calculated as the time from randomisation until last follow-up. Multiple linear regression will be used to assess the difference between the treatments arms, with centre as a random effect, before and after adjustment for age, ulcer size and ulcer chronicity (Table 8). Graphical methods will be used to assess whether the assumption of normality is met. If the assumption of normality is not met, and there is no suitable transformation, ulcer free time will be categorized (by quartiles) and the analysis will instead be performed using ordinal regression. Model fit will be assessed using residual plots and/or goodness-of-fit tests, as appropriate. The 24-week healing rate and associated 95% confidence interval will be obtained from the Kaplan-Meier analysis (4.3). The primary analysis will be based on study participants with at least 1 year of follow up only (as explained in 2.2). As a sensitivity analysis we will repeat the above regression model (adjusted for age, ulcer size and ulcer chronicity, and centre) using all the study participants, irrespective of length of follow up.

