#### **4.9 Derived Variables**

1. Deep vein reflux is defined as iliac, femoral, popliteal or crural deep vein reflux detected by Duplex scan.
2. Deep vein obstruction is defined as iliac, femoral, popliteal or crural deep vein outflow obstruction detected by Duplex scan.
3. Time to ulcer healing will be calculated as the difference between the final healing date and date of randomisation. Final healing date is collected in the InForm database and this variable is entered by trial manager after experts agree on the healing date. Patients will be censored at the time of last follow-up if they are dead, withdrawn or lost to follow-up before primary ulcer healing. The follow-up time is one year after randomisation and thus patients with unhealed primary ulcer at one year after randomisation will be also censored.
4. One-year ulcer free time will be calculated as total follow-up time in days (i.e. one year or time to the last follow-up if patients are dead, withdrawn or lost to follow before one year) deducting the total duration of ulcers, including primary ulcer and recurrences.
5. Ulcer chronicity will be calculated as the difference between the date of current ulcer appeared and the date of randomisation.

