## 5. Sensitivity analysis

As a sensitivity analysis, we will perform a per-protocol analysis by excluding patients with protocol violations. This sensitivity analysis will cover all primary and secondary outcomes. As the per-protocol analysis leads to the optimal effect of EVRA and could bring attrition bias, we will interpret the results of pre-protocol analysis with extreme caution. The surgeon data is collected separately and not included in the InForm database. If the surgeon data can be merged into the main database and, we will carry out another sensitivity analysis by including surgeon as a random effect in the Cox regression analysis for primary outcome.

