Pathophysiologic dysfunction		
Reflux		
Obstruction		
Both		
No venous cause		
VCSS Score		
Palpable pedal pulses		
Yes		
No		

\* Data presented as frequency (percentage) for categorical variables and median (range) for continuous variables

†A patient can have both deep vein reflux and obstruction

Table 5 Treatment summary

	EVRA N=	Standard N=
Endothermal only		
Foam only		
Mechanochemical ablation (MOCA) only		
Endothermal and Foam		
MOCA and Foam		

\* *Data presented as frequency (percentage)*

Table 6 Time to ulcer healing in patients with chronic venous ulceration (Cox regression model)

	Univariate model*		Multivariate model†	
	HR (95% CI)	P value	HR (95% CI)	P value
Treatment				
Standard arm				
EVRA				
Age (yrs)				
Ulcer chronicity (mths)				
Ulcer size				
1 st Quartile				
2 nd Quartile				
3 rd Quartile				
4 th Quartile				

\* Adjusted by centre (centre included in the model as a random effect)

† Adjusted by centre, age, ulcer size and chronicity (centre included in the model as random effect and age, ulcer size and chronicity as fixed effects).

Table 7 Summary of 12-week and 24-week ulcer healing rate and ulcer free time\*

	EVRA N=	Standard N=
12-week ulcer healing rate		
24-week ulcer healing rate		
No. of patients with recurrent ulcer		
Ulcer free time		

\* Data presented as frequency (percentage) for categorical variables and median (range) for continuous variables

Table 8 Multiple linear regression (ordinal regression) for ulcer free time (days) to 1 year in patients with chronic venous ulceration

	Univariate model*		Multivariate model†	
	Coefficient (95% CI)	P value	Coefficient (95% CI)	P value
Treatment				
Standard arm				
EVRA				
Age (yrs)				
Ulcer chronicity (mths)				
Ulcer size				
1 st Quartile				
2 nd Quartile				
3 rd Quartile				
4 th Quartile				

\* Adjusted by centre (centre included in the model as a random effect)

† Adjusted by centre, age, ulcer size and chronicity (centre included in the model as random effect and age, ulcer size and chronicity as fixed effects).

Table 9 Summary of quality of life (AVVQ, EQ-5D, SF36) at baseline, 6 weeks, 6 months and 12 months after randomisation

	N	EVRA	Standard
		Mean (SD)	Mean (SD)
AVVQ			
Baseline			
6 weeks			
6 months			
12 months			

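### Deaths before healing are censored and the 24-week healing rate is read from Kaplan-Meier, so the reported rate may slightly overstate the proportion of patients who actually heal

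*SAP*

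**What the plan says.** SAP 2.6 treats death like withdrawal and loss to follow-up: "Subjects who die, withdraw from the study, or are lost to follow-up before ulcer healing will be censored in the Kaplan Meier". The same applies to the Cox analyses, and the censoring date is the last follow-up visit. SAP 4.9, item 3, repeats the rule: "Patients will be censored at the time of last follow-up if they are dead, withdrawn or lost to follow-up before primary ulcer healing". Patients still unhealed at one year are also censored.

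SAP 4.5 then says: "The 24-week healing rate and associated 95% confidence interval will be obtained from the Kaplan-Meier analysis". It cites section 4.3 for this, but 4.3 is the treatment summary and the Kaplan-Meier analysis is in 4.4. Figure 3 shows the curve.

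Table 7 lists 12-week and 24-week healing rates, with the footnote: "Data presented as frequency (percentage) for categorical variables and median (range) for continuous variables". The 12-week rate appears only there, and the text names no estimator for it.

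SAP 2.4 excludes imputation: "There will be no data imputation for missing data in the primary endpoint (time to healing) and the secondary endpoints of 24-week healing rate". Ulcer free time is treated likewise. SAP 5 says: "As a sensitivity analysis, we will perform a per-protocol analysis by excluding patients with protocol violations". It adds a surgeon random effect if those data can be merged. Neither document plans a competing-risk estimate.

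**The concern.** Censoring assumes that a patient who leaves the risk set could still have the event later, at the same rate as those who remain. That can be defended for a withdrawn patient, who may heal unseen. It cannot hold for a patient who has died with an open ulcer. Kaplan-Meier passes that patient's weight to survivors who may yet heal, so one minus Kaplan-Meier describes a population in which nobody dies.

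Deaths are plausible here. Protocol 1.1.2 refers to patients with "chronic venous ulceration, who are often elderly, have extensive co-morbidities", and Protocol 4.4 lists death as an end of follow-up. The 24-week rate is a named secondary outcome, reported so that it can be compared with other studies (Protocol 4.3.2), and readers will take it as the share of patients healed.

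What is at stake is the absolute rate in each arm. The test of the primary hypothesis is not in question.

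**Working it through.** **The plan's own figures.** Protocol 7.1 assumes 60% v 75% healed at 24 weeks, 90% power and 10% dropout, and states 416 subjects and 254 healed ulcers. With proportional hazards, HR = ln(0.25)/ln(0.40) = 1.513. Freedman's formula gives 253 events. Then 253/0.675 = 374.8 evaluable patients, and 374.8/0.9 = 416.5. The stated figures reproduce closely, so 60% and 75% are used below as the Kaplan-Meier values.

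**Assumptions.** The documents give no mortality rate. I take 3% to 10% a year, equal in both arms, with constant hazards of healing and death.

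**Formula.** Let p be the Kaplan-Meier healing proportion at 24 weeks and q the probability of death by then. Put h = -ln(1-p) and d = -ln(1-q).

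- Kaplan-Meier, deaths censored: p
- Cumulative incidence: [h/(h+d)] × [1 - (1-p)(1-q)]

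**Example at 10% a year.** 1-q = 0.90^(24/52) = 0.9525, so d = 0.0486.

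- Standard arm: h = 0.9163; (0.9163/0.9649) × (1 - 0.40 × 0.9525) = 0.588
- Early arm: h = 1.3863; (1.3863/1.4349) × (1 - 0.25 × 0.9525) = 0.736

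| Annual mortality, both arms | Standard: KM v cumulative incidence | Early: KM v cumulative incidence | Overstatement (points) | Shift in difference between arms (points) |
|---|---|---|---|---|
| 3% | 60.0 v 59.6 | 75.0 v 74.6 | 0.4 and 0.4 | under 0.1 |
| 10% | 60.0 v 58.8 | 75.0 v 73.6 | 1.2 and 1.4 | 0.2 |

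**Unequal mortality.** Here q is set directly, at 2% in one arm and 5% in the other by 24 weeks.

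- 2% standard, 5% early: 73.5 - 59.5 = 14.0 points
- 5% standard, 2% early: 74.4 - 58.7 = 15.7 points

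**Right-hand end of Figure 3.** Extending the constant hazards to 52 weeks at 10% annual mortality gives 86.3 v 83.2 and 95.0 v 92.3, a gap of about 3 points. The documents do not support constant hazards beyond 24 weeks, so this shows only that the gap widens with time.

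**Precision.** With 208 per arm, the 95% half-width is 1.96 × √(0.60 × 0.40/208) = 6.7 points at 60% and 1.96 × √(0.75 × 0.25/208) = 5.9 points at 75%.

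**The Table 7 reading.** A raw percentage of all randomised patients keeps deaths in the denominator, but it also counts every withdrawal as unhealed. With 10% withdrawing by 24 weeks, independently of healing, and no deaths, the same formula with q = 0.10 gives raw percentages of 57.4 and 72.0 where Kaplan-Meier gives 60 and 75. The two readings of the SAP can therefore differ by more than the effect of deaths.

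**The case against.** The strongest reply is that this is a choice of estimand. Healing as if nobody died is a legitimate quantity, neither document says that the proportion actually healed is the target, and Kaplan-Meier suits comparison with earlier trials. That stands, and it is a reason to keep Kaplan-Meier. It does not remove the need to say which quantity the 24-week rate represents.

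The size is also assumed, and it is small against a half-width of about 6 to 7 points. Entry criteria (short ulcer duration, ABPI of at least 0.8, tolerance of compression) may select patients with lower mortality than venous ulcer patients in general. This stands too. However, the overstatement due to deaths always has the same sign, and a larger sample would not remove it.

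Deaths are partly visible already, in Table 12 and through the CONSORT diagram. Neither is specified to separate deaths before healing from deaths after it.

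A reader might infer several stronger points that the documents do not support:

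- **The hazard ratio or log-rank test is wrong.** It is not; both compare cause-specific healing rates.
- **The decision model is biased.** Protocol 7.5 describes its inputs as transition rates between states, and censoring at death estimates these properly. SAP 2.1 leaves health economics out of the SAP.
- **A one-year rate is overstated.** None is tabulated; only the plotted curve is affected.
- **The 12-week rate is overstated.** SAP 4.5 assigns only the 24-week rate to Kaplan-Meier.
- **The net direction of all censoring bias is known.** It is known for deaths only. Informative withdrawal could act either way.

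**Conclusion.** The point holds as a minor one. As written, the 24-week rate and the Figure 3 curve describe healing without deaths, and may slightly overstate the proportion of patients who heal. Under 3-10% annual mortality, equal in both arms, constant hazards and 60%/75% healing, the 24-week overstatement is about 0.4-1.4 points per arm, and the difference between arms moves by about 0.2 points or less. That last limit depends on equal mortality: with 2% v 5% by 24 weeks, the difference would be about 14.0 or 15.7 points instead of 15. No effect on the primary test or the sample size is claimed. Separately, SAP 4.5 and the Table 7 footnote allow two different 24-week rates, and this needs settling whatever the mortality.

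**What to change.** - In SAP 4.5 and Table 7, report the 24-week cumulative incidence of healing by arm, with death as a competing event (Aalen-Johansen) and a 95% confidence interval. Show the Kaplan-Meier value alongside for comparison with earlier trials.
- Use the same estimator for the 12-week rate, and say so in the text.
- Show the cumulative incidence curve with Figure 3.
- Report the number of deaths before healing by arm.
- Replace the Table 7 footnote for the healing rates with the named estimator, and correct the cross-reference in SAP 4.5 from 4.3 to 4.4.
- Keep the Cox model and log-rank test, and describe them as a cause-specific comparison.

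The cost is some SAP wording, one standard procedure and slightly lower stated healing rates. Fatal events up to 12 months are already entered in InForm as serious adverse events (Protocol 8.4). The documents do not say that the date of death is held as a separate item, so confirm this, because SAP 2.6 censors at the last follow-up visit.
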